## VERSION HISTORY

Version	Version Date	Description
1.0	07 December 2021	Original signed version
1.1	15 February 2022	

• Added data source of mycological results

• Updated definition of mycological response

• Updated reasons to exclude from MPP

• Updated calculation of days of exposure

• Updated calculation of overall compliance

• Updated definition of TEAE

## LIST OF ABBREVIATIONS

Abbreviation	Definition
AE	Adverse Event
ATC	Anatomical Therapeutic Chemical
CITT	Clinical intent-to-treat
CSR	Clinical Study Report
eCRF	Electronic Case Report Form
EDC	Electronic Data Capture
EOT	End-of-treatment
ITT	Intent-to-treat
IWRS	Interactive Web Response System
LOCF	Last post-baseline observation carried forward
MedDRA	Medical Dictionary for Regulatory Activities
MITT	Mycological Intent-to-Treat
MPP	Mycological Per-Protocol
SAE	Serious Adverse Event
SAP	Statistical Analysis Plan
TEAE	Treatment-emergent Adverse Event
TOC	Test-of-cure
TSSS	Total signs/symptoms score
WHO	World Health Organization

## 1 INTRODUCTION

The purpose of this Statistical Analysis Plan (SAP) is to provide a description of the statistical methods to be implemented for the analysis of data from the study with protocol numbers CLOTOT3-16IA01 (CLEAR-1) version 2.0 (Amendment 1) and CLOTOT3-16IA03 (CLEAR-2) version 2.0 (Amendment 1). The SAP will be finalized prior to database lock. Any deviations from the SAP after database lock will be documented in the final Clinical Study Report (CSR).

## 2 STUDY OVERVIEW

### 2.1 Study Objectives

#### 2.1.1 Primary Objective

To demonstrate the superior efficacy of Clotrimazole vs. placebo in the treatment of otomycosis, with respect to the therapeutic cure at test-of-cure (TOC; Visit 4) in the mycological intent-to-treat (MITT) population.

**Therapeutic cure** is defined as both mycological cure AND clinical cure.

**Mycological cure** is defined as eradication (culture does not show growth of any fungal pathogen) or presumed eradication (there is no material to culture and the overall clinical outcome is clinical cure)

**Clinical cure** is defined as a total signs/symptoms score (TSSS) of zero on a 4-point scale for pruritus, otalgia, ear fullness and otorrhea.

No Response is defined as:

- a positive fungal culture (i.e., identification of a fungal pathogen from fungal and/or bacterial cultures) OR
- sum of signs and symptoms  $>0$  on TOC

#### 2.1.2 Secondary Objectives

- Overall clinical cure at Visits 2, 3 and 4.
- Mycological cure at Visits 2, 3 and 4.
- Therapeutic cure at Visit 2 and 3.
- Changes in TSSS at Visits 2, 3 and 4.
- Changes in individual signs and symptoms at Visits 2, 3 and 4.

In the case of bilateral otomycosis the non-selected ear will also be treated and assessed for its clinical evolution.

### 2.2 Study Design

#### 2.2.1 Overview

This is a randomized, parallel-group, double-blinded, active-controlled, multicenter study comparing Clotrimazole 1% otic solution with Placebo in the treatment of fungal otitis externa (otomycosis) in adults. A diagram of the study design is shown in Figure 1, and the schedule of observations and procedures is shown in Table 1.

Patients selected for the study will be male or female, 18 years of age and older, with uncomplicated otomycosis in at least 1 ear. At Visit 1 (Day 1), patients who have signed the Informed Consent Form (or had it signed by their legally authorized representative) and met the study entry criteria will be randomized in a 2:1 ratio to either the investigational treatment, Clotrimazole 1% otic solution, or the Placebo, Saline solution 0.9%.

At these visits, signs and symptoms of otomycosis will be assessed and a sample of ear exudate (otorrhea or debris if otorrhea is not available) for bacterial and mycological cultures will be collected before onset of treatment and debridement. Debridement of the ear will be preferably done by suction. Patients will be taught to administer study medication and will be instructed to apply it twice daily for 14 days. Patients will receive a 14-day supply of study medication. Patients with bilateral otomycosis will receive the same treatment in both ears. Patients will be instructed to refrain from swimming during the study treatment period and preferably until the final study visit is completed. Patients will also be advised to use a shower cap or neoprene band when bathing.

Day 1 will be the day when the first dose is administered (important when the first dose is administered the day after the baseline visit).

At Visit 1, a urine pregnancy test will be performed in females of childbearing potential.

Patients who show up before day 8 with no improvement or worsening of their signs/symptoms, and the investigator's decision is to discontinue the patient from the study medication, this will be considered as Visit 2, and all the procedures corresponding to this visit will apply.

Patients will attend Visit 2 on Day 8-10 of study treatment to check on each patient's clinical progress. At this visit, signs and symptoms of otomycosis will be assessed and otorrhea sample will be collected if exudate is present. In the case of patients who report no improvement in otomycosis signs/symptoms at Visit 2 (Day 8-10), the Investigator will choose one of the two following options for the patient:

[figure not shown]
1. Continue with the study medication. Patient continues in the study and attends visit 3.
2. Discontinue study medication. The Investigator may treat patient with other medication (rescue medication) at their discretion.
  - If investigator prescribes rescue medication, the patient will be withdrawn from the study. The clinical outcome for the patient will be recorded as Treatment failure at the End of Study form.
  - If investigator does not prescribe any rescue medication, the patient will be expected to return for a clinical and safety evaluation at Visit 3.

Non-discontinued patients will attend Visit 3 (EOT: end-of treatment) and Visit 4 (TOC: test-of-cure) at approximately Day 15 and Day 24, respectively. At these visits, signs and symptoms of otomycosis will be assessed and ear exudate, if present, will be collected for bacterial and mycological cultures. The primary efficacy endpoint will be the proportion of patients with Therapeutic cure (Clinical cure + Mycological Cure) at Test of Cure (Visit 4).

In the case of patients who report no improvement in otomycosis signs/symptoms at Visit 3 (Day 15-17), the Investigator will choose one of the two following options for the patient:

1. Continue the patient in the study without any rescue medication until Visit 4 (Day 24-26). The patient will come to Visit 4.
2. Prescribe rescue medication and withdraw the patient from the study. The clinical outcome for the patient will be recorded as Treatment Failure at the End of Study form.

**Figure 1** Diagram of Study Design

**Table 1 Schedule of Observations**

Evaluation	Visit 1 Screening (Study Entry)	Visit 2 On treatment	Visit 3 End of Treatment	Visit 4 Test of cure
Study Day	1	8-10	15-17	24-26
Informed Consent	X			
Inclusion/exclusion criteria	X			
Medical history	X			
Concurrent symptoms/conditions	X			
Urine pregnancy test a	X			
Physical examination b	X			
Vital signs c	X	X	X	X
Pruritus	X	X	X	X
Otalgia	X	X	X	X
Ear fullness	X	X	X	X
Otorrhea	X	X	X	X
Overall Clinical Outcome		X	X	X
Bacterial and Mycological cultures of ear discharge	X	X d	X d	X d
Debridement of the ear	X	X d	X d	X d
Randomization through IWRS	X			
Dispense study medication and explain its use	X	X e		
Provide a visit calendar	X			
Collect used and unused study medication containers			X f	
Concomitant medications	X	X	X	X
Adverse events	X	X	X	X

a For female patients of childbearing potential.

b To include a directed examination of the ears, head, nose and oropharynx.

c To include temperature, blood pressure, and pulse rate.

d If no discharge (otorrhea or debris) is present, no attempt to culture will be made.

e If patient with unilateral otomycosis at baseline becomes bilateral prior to Visit 3 a resupply study medication kit (with the same medication) will be dispensed for the non-evaluable ear.

f If patients forget to bring in containers at this visit, they must bring them in no later than Visit 4.

## 2.2.2 Patient Identification and Randomization

Patients will be randomized at Visit 1, after signing informed consent and meeting eligibility criteria. Randomization will be conducted through an Interactive Web Response System (IWRS) include blocking. The IWRS will assign a patient number, which will be used to identify the patient during screening and, if applicable, throughout the duration of the study. Patients who do not meet the inclusion and exclusion criteria will be registered as screen failures through the IWRS.

For patients who have bilateral otomycosis, the ear with a higher TSSS (as defined in Section 2.3.1.1.5) will be considered the evaluable one. If the TSSS is identical in both ears, the left ear will be selected as the evaluable ear. In either case, the non-evaluable ear will receive the same treatment as the evaluable ear.

### 2.2.3 *Blinding and Breaking the Blind*

All study medication products (test and placebo) will have the same packaging and labels.

The boxes in which the study medication is packaged, shipped, and dispensed will be identical in appearance. When patients return their used and unused study medication containers to the study site, they will be encouraged to bring them in the original carton.

Mycological and bacterial samples will be processed by a central laboratory under blinded conditions. The central laboratory will be blinded to the treatment assignment of the patient from whom the sample was taken.

Unblinding of study treatment assignment should be an unusual occurrence, and should be done only in case of an emergency when knowledge of the actual treatment becomes medically necessary to affect treatment options. The investigator will be able to break the blind and get the subject's treatment assignment through IWRS at any time, by completing the required information. The investigator should not share the unblinded information with Laboratorios Salvat, S.A. (Salvat) or [REDACTED] personnel.

### 2.2.4 *Sample Size Determination*

Planned enrollment is 191 patients randomized in 2:1 ratio (Clotrimazole 1% otic solution: Placebo) to obtain 150 evaluable patients (100 Clotrimazole 1% and 50 Placebo) for each trial.

Clotrimazole otic solution should be statistically superior to the placebo ( $p<0.05$ ) with regard to the therapeutic cure at the test-of-cure visit, using the MITT population.

Assuming a significance level of 5% and a desired statistical power of 95%, a placebo effect of 30%, and a 2:1 allocation schedule, the total number of patients needed to detect a difference of 30% in the therapeutic cure (100% relative increase) is 150 (100 with clotrimazole and 50 with placebo). The suspected dropout rate due to negative mycological culture at baseline is 21% that leads to a required inclusion of 191 patients (127 for the clotrimazole group and 64 patients for the placebo group).

As CLEAR-1 and CLEAR-2 are twin trials, if one of them is completed before the other, an updated sample size computation will be performed for the latter in order to have a more accurate picture of treatment and control arm success probabilities.

## 2.3 Study Endpoints

### 2.3.1 *Efficacy Parameters*

#### 2.3.1.1 *Clinical Efficacy Parameters*

##### 2.3.1.1.1 *Pruritus*

Pruritus in both ears will be assessed by the investigator at all visits. For consistency, the same individual should perform all the assessments at all visits, if possible. Pruritus will be assessed as:

- Severe (3) if pruritus is marked or intense
- Moderate (2) if pruritus is definitely present
- Mild (1) if pruritus is slight
- Absent (0) if there is complete absence of pruritus

At Visits 2, 3 and 4, pruritus will be considered resolved if the level is 0. Pruritus will be considered improved if the level is lower than the previous pruritus assessment.

#### 2.3.1.1.2 Oinalgia

Oinalgia in both ears will be assessed at all visits. The investigator will ask the patient to assess his or her level of otalgia on the day of the visit. If the patient has taken analgesic medication, he or she will be asked to assess the level of otalgia before taking the analgesic. For consistency, the assessment of otalgia should always be performed before the ear is examined. Assessments will be on the scale described in Blanch 2000. Oinalgia will be assessed as:

- Severe (3) if it interferes with activities of daily living;
- Moderate (2) if it causes discomfort but does not interfere with activities of daily living;
- Mild (1) if there is awareness of pain but not much discomfort; or
- Absent (0) if there is total absence of pain.

At Visits 2, 3 and 4, oinalgia will be considered resolved if the level is 0. Oinalgia will be considered improved if the level is lower than the previous oinalgia assessment.

#### 2.3.1.1.3 Ear fullness

Ear fullness (aural fullness or ear pressure) in both ears will be assessed by the investigator at all visits. For consistency, the same individual should perform all the assessments at all visits, if possible. Ear fullness will be assessed as:

- Severe (3) if ear fullness, is marked or intense
- Moderate (2) if ear fullness is definitely present
- Mild (1) if ear fullness is slight
- Absent (0) if there is complete absence of ear fullness

At Visits 2, 3 and 4, ear fullness will be considered resolved if the level is 0. Ear fullness will be considered improved if the level is lower than the previous ear fullness assessment.

#### 2.3.1.1.4 Otorrhea

Otorrhea in both ears will be assessed by the investigator at all visits. For consistency, the same individual should perform all the assessments at all visits, if possible. Otorrhea will be assessed as:

- Severe (3): copious discharge that prevents visualization of the tympanic membrane unless the fluid is suctioned
- Moderate (2): the anterior sulcus is full, but the tympanic membrane is still clearly visible
- Mild (1): little fluid accumulating in the anterior tympanomeatal sulcus but the tympanic membrane is still visible
- Absent (0) absence of fluid

At Visits 2, 3 and 4, otorrhea will be considered resolved if the level is 0. Otorrhea will be considered improved if the level is lower than the previous otorrhea assessment.

#### 2.3.1.1.5 Overall Clinical Outcome

Overall Clinical Outcome is based on the TSSS, which is calculated by the sum of pruritus score + oinalgia score + ear fullness score + otorrhea score. Patients will be allocated to one of the following categories for Overall Clinical Outcome:

1. Clinical Cure: TSSS is 0, as defined in Sections 2.3.1.1, 2.3.1.2, 2.3.1.3 and 2.3.1.4.
2. Clinical Improvement: TSSS is different than 0 but lower than the previous visit, as defined in Sections 2.3.1.1, 2.3.1.2, 2.3.1.3 and 2.3.1.4.

3. Clinical Failure: TSSS does not meet the definitions of Clinical Cure or Clinical Improvement, as defined in Sections 2.3.1.1.1, 2.3.1.1.2, 2.3.1.1.3 and 2.3.1.1.4.
4. Not changed: TSSS is different than 0 but unchanged compared to the previous visit.
5. Indeterminate: Discontinued (for reasons other than Clinical Failure) or lost to follow up.
6. Not applicable: In case of the non-evaluable ear in patients with unilateral otomycosis or at Visit 2 a new occurrence of otomycosis is determined in the non-evaluable ear and the unilateral otomycosis becomes bilateral.

Patients who take rescue medication (as defined in Protocol Section 6.7.2) will be considered Clinical Failures.

### *2.3.1.2 Mycological Efficacy Parameters*

#### *2.3.1.2.1 Mycological Outcome*

Samples of ear discharge will be taken at V1, and in addition at visits V2, V3 and V4, when discharge is present. The otorrhea/debris sample will be taken prior to the debridement of the affected ear. A central laboratory will provide exudate sampling kits with standardized instructions for sample preparation (as defined in the Laboratory manual).

The otorrhea/debris sample will be sent to the Central Laboratory for processing. The central laboratory will be blinded to the treatment assignment of the patient from whom the sample was taken.

The central laboratory will use standardized microbiological laboratory procedures to identify fungal and bacterial species. If the culture does not show growth of any fungal pathogen from central laboratory or the local laboratory sent the wrong organism to central laboratory, the mycological result from local laboratory will be used.

Susceptibility testing will be performed on fungal isolates that are present at baseline and TOC for an individual subject according the Clinical and Laboratory Standard Institute methods for clotrimazole and comparator drugs to which the fungal isolates are susceptible.

For any patient with a culture positive for fungi at Visit 1, mycological outcome at Visit 2 will be classified as:

- Eradication if the culture does not show growth of any fungal pathogen;
- Presumed Eradication if there is no material to culture and the Overall Clinical Outcome is Clinical Cure;
- Persistence if any fungal pathogen cultured at Visit 1 is still present;
- Presumed Persistence: if there is no material to culture or sample was not taken or sample was not shipped to lab and the Overall Clinical Outcome is not Clinical Cure;
- Superinfection if a new fungal pathogen not present at Visit 1 is isolated while the initial pathogen is also present (presence of a nonpathogenic organism will not be considered Superinfection);
- Reinfection: if there is isolation of a new fungal pathogen different from the one present at Visit 1 and the initial pathogen is not present; or
- Indeterminate if none of the above definitions are met and the mycological outcome cannot be determined.

For any patient with a culture positive for fungi at Visit 1, mycological outcome at Visit 3 will be classified as:

- Eradication if the culture does not show growth of any fungal pathogen;

- Presumed Eradication if there is no material to culture and the Overall Clinical Outcome is Clinical Cure;
- Persistence if any fungal pathogen cultured at Visit 1 is still present;
- Presumed Persistence: if there is no material to culture or sample was not taken or sample was not shipped to lab and the Overall Clinical Outcome is not Clinical Cure;
- Recurrence: if there is reappearance of the fungal pathogen present at Visit 1 which was eradicated or presumably eradicated at Visit 2;
- Superinfection if a new fungal pathogen not present at Visit 1 is isolated while the initial pathogen is also present (presence of a nonpathogenic organism will not be considered Superinfection);
- Reinfection: if there is isolation of a new fungal pathogen different from the one present at Visit 1 and the initial pathogen is not present; or
- Indeterminate if none of the above definitions are met and the mycological outcome cannot be determined.

For any patient with a culture positive for fungi at Visit 1, mycological outcome at Visit 4 will be classified as:

- Eradication if the culture does not show growth of any fungal pathogen;
- Presumed Eradication if there is no material to culture and the Overall Clinical Outcome is Clinical Cure;
- Persistence if any fungal pathogen cultured at Visit 1 is still present;
- Presumed Persistence: if there is no material to culture or sample was not taken or sample was not shipped to lab and the Overall Clinical Outcome is not Clinical Cure;
- Recurrence: if there is reappearance of the fungal pathogen present at Visit 1 which was eradicated or presumably eradicated at Visit 2 and/or 3;
- Superinfection if a new fungal pathogen not present at Visit 1 is isolated while the initial pathogen is also present (presence of a nonpathogenic organism will not be considered Superinfection);
- Reinfection: if there is isolation of a new fungal pathogen different from the one present at Visit 1 and the initial pathogen is not present; or
- Indeterminate if none of the above definitions are met and the mycological outcome cannot be determined.

Mycological outcome will be determined for each patient for Visit 2, Visit 3 and for Visit 4 after mycological culture results are made available to the Sponsor or designee.

Mycological cure is defined as eradication (culture does not show growth of any fungal pathogen) or presumed eradication (there is no material to culture and overall clinical outcome is clinical cure).

For any patient with non fungal pathogen at Visit 1, mycological response at Visit 2 will be classified as:

- Presumed Eradication if the culture does not show growth of any fungal pathogen or if there is no material to culture and the Overall Clinical Outcome is Clinical Cure;
- Presumed Persistence if the Overall Clinical Outcome is Clinical Failure but no culture result is available;
- Superinfection if a pathogen not present at Visit 1 is now present; or
- Indeterminate if none of the above definitions are met and the mycological response cannot be determined.

For any patient with non fungal pathogen at Visit 1, mycological response at Visit 3 will be classified as:

- Presumed Eradication if the culture does not show growth of any fungal pathogen or if there is no material to culture and the Overall Clinical Outcome is Clinical Cure;
- Presumed Persistence if any fungal pathogen cultured at Visit 2 is still present or if the Overall Clinical Outcome is Clinical Failure but no culture result is available;
- Superinfection if a pathogen not present at Visit 1 and Visit 2 is now present;
- Indeterminate if none of the above definitions are met and the mycological response cannot be determined.

For any patient with non fungal pathogen at Visit 1, mycological response at Visit 4 will be classified as:

- Presumed Eradication if the culture does not show growth of any fungal pathogen or if there is no material to culture and the Overall Clinical Outcome is Clinical Cure;
- Presumed Persistence if any fungal pathogen cultured at Visit 2 and 3 is still present or if the Overall Clinical Outcome is Clinical Failure but no culture result is available
- Recurrence if a pathogen isolated at Visit 2, which was not present at Visit 3, reappears at Visit 4
- Superinfection if a pathogen not present at Visit 1, Visit 2 and Visit 3 is now present;
- Indeterminate if none of the above definitions are met and the mycological response cannot be determined.

The above rules will be used for microbiological outcome summaries for the patients in the clinical intent-to-treat (CITT) populations that have no pathogen at Visit 1, since mycological response cannot be calculated without any pathogen at Visit 1.

If Overall Clinical Outcome at Visit 2, 3 or 4 (follow up visits) is Clinical Failure (whether or not the patient discontinues prematurely) and no mycological culture is performed at one of those follow-up visits, the mycological response at that follow-up visit will be Presumed Persistence.

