6.4 Blinding and Breaking the Blind

All study medication products (test and placebo) will have the same packaging and labels.

The boxes in which the study medication is packaged, shipped, and dispensed will be identical in appearance. When patients return their used and unused study medication containers to the study site, they will be encouraged to bring them in the original carton.

Mycological and bacterial samples will be processed by a central laboratory under blinded conditions. The central laboratory will be blinded to the treatment assignment of the patient from whom the sample was taken.

Unblinding of study treatment assignment should be an unusual occurrence, and should be done only in case of an emergency when knowledge of the actual treatment becomes medically necessary to affect treatment options. The investigator will be able to break the blind and get the subject's treatment assignment through ITRS at any time, by completing the required information (e.g the user's password, the patient code concerned by the unblinding request, unblinding

code...). The investigator should not share the unblinded information with SALVAT or [REDACTED] personnel.

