7.1.2 Mycological Efficacy Parameters

7.1.2.1 Mycological Outcome

Samples of ear discharge will be taken at V1, and in addition at visits V2, V3 and V4, when discharge is present. The otorrhea/debris sample will be taken prior to the debridement of the affected ear. A central laboratory will provide exudate sampling kits with standardized instructions for sample preparation (as defined in the Laboratory manual).

The otorrhea/debris sample will be sent to the Central Laboratory for processing. The central laboratory will be blinded to the treatment assignment of the patient from whom the sample was taken.

The central laboratory will use standardized microbiological laboratory procedures to identify fungal and bacterial species.

Susceptibility testing on fungal isolates will be performed according the Clinical and Laboratory Standard Institute methods for clotrimazole and comparator drugs to which the fungal isolates are susceptible.

For any patient with a culture positive for fungi at Visit 1, mycological outcome at Visit 2 will be classified as:

- Eradication if the culture does not show growth of any fungal pathogen;
- Presumed Eradication if there is no material to culture and the Overall Clinical Outcome is Clinical Cure;
- Persistence if any fungal pathogen cultured at Visit 1 is still present;
- Presumed Persistence: if there is no material to culture and the Overall Clinical Outcome is not Clinical Cure;
- Superinfection if a fungal pathogen not present at Visit 1 is now present (presence of a nonpathogenic organism will not be considered Superinfection); or
- Indeterminate if none of the above definitions are met and the mycological outcome cannot be determined.

For any patient with a culture positive for fungi at Visit 1, mycological outcome at Visit 3 will be classified as:

- Eradication if the culture does not show growth of any fungal pathogen;
- Presumed Eradication if there is no material to culture and the Overall Clinical Outcome is Clinical Cure;
- Persistence if any fungal pathogen cultured at Visit 1 is still present;
- Presumed Persistence: if there is no material to culture and the Overall Clinical Outcome is not Clinical Cure;
- Recurrence: if there is reappearance of the fungal pathogen eradicated or presumably eradicated at Visit 2;
- Superinfection if a new fungal pathogen is isolated while the initial pathogen is also present (presence of a nonpathogenic organism will not be considered Superinfection);

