## 3 STATISTICAL METHODOLOGY

### 3.1 General Considerations

#### 3.1.1 Definition of Baseline

For microbiological data, baseline pathogen(s) are determined from the samples collected prior to the first dose of study drug.

For all efficacy and safety endpoints, baseline is defined as the last measurement or assessment prior to the first dose of study drug.

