#### *3.3.2 Protocol Deviations*

Protocol deviations are defined as violations from the procedures outlined in the protocol. Major protocol deviations are protocol violations likely to affect the study results and leading to the exclusion of the subject from the MPP.

Once the database has been completed and considered as “clean”, a data blind review will be conducted before the database lock in order to identify all major protocol violations and assign subjects into each of the analysis sets as defined in Section 3.2.

Patients with protocol deviations will be presented in the data listings. Counts and percentages of subjects with protocol deviations by deviation category will be summarized by treatment and in total based on CITT population.

The protocol deviations are considered critical (or very serious) and major (or serious), according to the following definitions:

- Critical or very serious: Deviations affecting / they have adversely affected the rights, safety or welfare of subjects and / or the quality and integrity of data
- Major or serious: Deviations that may affect / have adversely affected the rights, safety or welfare of subjects and / or the quality and integrity of data.

In addition, the protocol deviations related to COVID-19 will be categorized and summarized by treatment and in total based on CITT population separately.

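### Does letting a local laboratory result replace a negative central culture undermine the primary analysis?

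*SAP*

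**What the plan says.** Protocol 6.4 states: "Mycological and bacterial samples will be processed by a central laboratory under blinded conditions". Protocol 7.1.2.1 states: "The otorrhea/debris sample will be sent to the Central Laboratory for processing", and has the central laboratory identify the species. Neither section mentions a local result. SAP 2.2.3 keeps the same position: "The central laboratory will be blinded to the treatment assignment of the patient from whom the sample was taken".

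SAP 2.3.1.2.1 then adds a fallback with two triggers: "If the culture does not show growth of any fungal pathogen from central laboratory or the local laboratory sent the wrong organism" to the central laboratory. In either case "the mycological result from local laboratory will be used". No visit is named.

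The culture enters the primary analysis twice. A positive baseline culture for *Aspergillus* or *Candida* puts a patient in the MITT population (SAP 3.2.3). A Visit 4 culture without fungal growth counts as eradication, which is one half of therapeutic cure (SAP 2.3.1.3 and 3.4.1).

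The SAP version history records for version 1.1 that a data source for mycological results was added. SAP Section 5, which lists changes from the protocol, does not mention the rule. The sensitivity analyses in SAP 3.4.1 are the standardized estimator, multiple imputation, a worst case and LOCF. The supportive analyses repeat the primary analysis in MPP and CITT.

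**The concern.** A blinded central laboratory is there to give one uniform reading of the culture. Here a second source, whose methods neither document describes, can overrule it, and the two directions are treated differently. A central negative gives way to a local positive. A central positive is replaced only if the wrong organism was sent. The no-growth trigger can therefore only add patients to MITT at baseline and can only turn a cure into a failure at Visit 4.

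The rule reaches both the population and the endpoint of the primary analysis, is absent from the list of protocol changes, and is not varied in any planned analysis. On that reading, the endpoint as the protocol sourced it would never be reported, and a result close to the significance threshold might depend on which laboratory was believed.

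**Working it through.** **The plan's own figure.** Inputs from SAP 2.2.4 and 3.4.1: 60% against 30% cure, 100 and 50 patients, two-sided 5% chi-square test.

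- Pooled rate: (60 + 15)/150 = 0.50.
- Standard error under the null: √(0.50 × 0.50 × (1/100 + 1/50)) = 0.0866.
- Standard error under the alternative: √(0.24/100 + 0.21/50) = 0.0812.
- Power: Φ((0.30 − 1.96 × 0.0866)/0.0812) = 94.6%, against the stated 95%.
- Enrolment: 100/0.79 = 126.6 and 50/0.79 = 63.3, rounded up to 127 + 64 = 191, as stated.

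**Baseline.** SAP 3.1.1 says "baseline pathogen(s) are determined from the samples collected prior to the first dose of study drug". Treatment cannot influence a pre-dose sample, so any difference between arms in local-only positives at baseline is due to chance. The rule can change who is in MITT, but it cannot bias the comparison within MITT through the baseline culture.

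The CITT repeat removes the baseline question altogether. CITT is all randomized patients (SAP 3.2.2). For a patient with a total score of zero at Visit 4, the two classification schemes in SAP 2.3.1.2.1 (fungal pathogen at Visit 1, or none) lead to the same therapeutic outcome:

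| Visit 4 culture, total score 0 | Fungal pathogen at Visit 1 | None at Visit 1 | Therapeutic cure |
|---|---|---|---|
| No fungal growth | Eradication | Presumed eradication | Yes in both |
| No material to culture | Presumed eradication | Presumed eradication | Yes in both |
| Fungal growth | An unfavorable category | An unfavorable category | No in both |

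A score above zero is a failure in either scheme. So the CITT result does not depend on which laboratory called the baseline culture positive. Its Visit 4 cultures still follow the fallback rule.

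**Visit 4.** For the no-growth trigger to change an outcome, four things must coincide:

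1. The total score is 0; otherwise the patient is already a failure.
2. Material remains to be cultured. Otorrhea must score zero, defined as "Absent (0) absence of fluid", so only debris is left; SAP Table 1, note d, has no culture attempted without discharge or debris.
3. The central culture shows no fungal growth.
4. The local culture shows a fungal pathogen.

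The number of reversals needed follows from the uncorrected chi-square, X² = N(ad − bc)²/(product of the four margins), with N = 150:

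| Cures, clotrimazole and placebo | X² | p |
|---|---|---|
| 60/100 and 15/50 (planned) | 150 × 1500²/(100 × 50 × 75 × 75) = 12.00 | 0.0005 |
| 47/100 and 15/50 | 150 × 850²/(100 × 50 × 62 × 88) = 3.97 | 0.046 |
| 46/100 and 15/50 | 150 × 800²/(100 × 50 × 61 × 89) = 3.54 | 0.060 |
| 46/100 and 14/50 | 150 × 900²/(100 × 50 × 60 × 90) = 4.50 | 0.034 |

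From the planned result, 60 − 46 = 14 clotrimazole cures must be reversed with none on placebo. That is 14/60 = 23% of the clotrimazole cures. The last two rows show the opposite case: if the result already lay near the threshold, a single placebo reversal would move p from 0.060 to 0.034.

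If the same share of cures were reversed in both arms (assumed, since no rate is given), the difference shrinks: 5% gives 57% against 28.5% and power 92.4%; 10% gives 54% against 27% and power 89.6%. Equal reversal therefore works against clotrimazole.

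**Section 5.** Other mycological changes are missing from it too: the scheme for patients without a fungal pathogen at Visit 1, the wording in SAP 2.1.1 that a positive result may come from a fungal or a bacterial culture, and the limit on which isolates undergo susceptibility testing. The list is incomplete in general; this rule was not singled out.

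**The case for a change.** The strongest case for a change is that a central-only run and a small table by arm cost little, leave the primary analysis alone, and would be more credible planned in advance than chosen after unblinding. The blind review ("a data blind review will be conducted before the database lock") is described for protocol violations and assignment to analysis sets; it does not mention the Visit 4 culture source or wrong-organism decisions. The CITT repeat still uses the fallback at Visit 4. Unequal reversal could also matter: with 15% of clotrimazole and 5% of placebo cures reversed, power would be 75.8%; with those shares exchanged, 96.7%.

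These statements are correct, but they do not show that a central-only run would be informative. If isolates are forwarded and fail to regrow, that run would drop infected patients at baseline and count surviving fungus as eradication at Visit 4. In wrong-organism cases the central result describes the wrong isolate. A disagreement between the two runs could not be read as evidence against the primary result. Unequal reversal needs a mechanism that differs by arm in a double-blind trial, and the documents suggest none.

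A further argument is that local-only positives could dilute the treatment effect in MITT. That would be a cost of having the rule at all. Adding a sensitivity run while keeping the rule recovers none of it.

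What stands is that Section 5 should have named the rule, and that a count of affected patients by arm would be informative. Both are matters of reporting. The rule is stated in the body of the SAP and signalled in its version history, and SAP Section 6 puts all available data in the listings, from which the count can be made.

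**Conclusion.** No change to the plan follows. The fallback departs from the protocol's wording and is missing from an incomplete list of changes, which is a clerical slip. As an analysis rule it is a fair trade-off: it guards against treating failed regrowth as absence of fungus, and at Visit 4 its no-growth trigger only makes cure harder to reach. At the planned rates, 14 reversals confined to clotrimazole are needed to lose significance. Only a result already close to p = 0.05 would be sensitive to one or two patients.

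This rests on three assumptions. Local laboratories culture first and forward isolates, as the wrong-organism wording suggests; the laboratory manual that would confirm it is not among the documents. The local reading is made without knowledge of treatment, which follows from the double-blind design but is not stated for local laboratories. Disagreement between laboratories at Visit 4 is uncommon among patients with a total score of zero; the documents give no rate, so its size and net direction remain unknown.
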